9.2 Sample Size Determination

The sample of 10 patients will provide >90% power to determine the expected success rate (80%) is greater than a theoretical placebo rate (20%).

9.3 Populations for Analysis

Both an Intentional-to-Treat (ITT) and per-protocol analysis will be performed.

9.4 Statistical Analysis

Descriptive statistics will be used to summarize the data. Categorical variables will be presented as number and percentage of total patients. Continuous variables will be summarized using mean, standard deviation, median and [Q1, Q3]. The proportion of patients with successful consumption of peanut protein without symptoms (primary endpoint), will be tested to determine whether the proportion differs from 0.2 (20%) (the expected success rate in a theoretical placebo group).

10. Supporting Documentation and Operational Considerations

10.1 Regulatory, Ethical and Study Oversight Considerations

10.1.1 Informed Consent Process

10.1.1.1 Consent/Accent and Other Informational Documents Provided to Participants

Consent forms describing in detail the study intervention, study procedures, and risks are given to the participant and written documentation of informed consent is required prior to starting intervention/administering study intervention. The following consent materials are submitted with this protocol:

- Informed Consent
- Informed Assent

10.1.1.2 Consent Procedures and Documentation

Informed consent is a process that is initiated prior to the individual and parent/guardian's agreeing to participate in the study and continues throughout the individual's study participation. Consent forms will be Pediatric ResearchReview Committee (PRRC) and Institutional Review Board (IRB)-approved and the participant and/or parent/guardian will be asked to read and review the document. The investigator will explain the research study to the participant and parent/guardian and answer any questions that may arise. A verbal explanation will be provided in terms suited to the participant and parent/guardian's comprehension of the purposes, procedures, and potential risks of the study and of their rights as research participants. Participants and parents/guardians will have the opportunity to carefully review the written consent form and ask questions prior to signing. The participants and parents/guardians should have the opportunity to discuss the study with their family or surrogates or think about it prior to agreeing to participate. The participant's parent/guardian will sign the informed consent document prior to any procedures being done specifically for the study. Participants and parents/guardians must be informed that participation is voluntary and that they may withdraw from the study at any time, without prejudice. A copy of the informed consent document will be given to the participant's parent/guardian for their records. The informed consent process will be conducted and documented in the source document (including the date), and the form signed, before the participant undergoes any study-specific procedures. The rights and welfare of the participants will be protected by emphasizing to them that the quality of their medical care will not be adversely affected if they decline to participate in this study

10.1.2 Study Discontinuation and Closure

This study may be temporarily suspended or prematurely terminated if there is sufficient reasonable cause. Written notification, documenting the reason for study suspension or termination, will be provided by the suspending or terminating party to <study participants, investigator, funding agency, the Investigational New Drug (IND) or Investigational Device Exemption (IDE) sponsor and regulatory authorities>. If the study is prematurely terminated or suspended, the Principal Investigator (PI) will promptly inform study participants, the Institutional Review Board (IRB), and sponsor and will provide the reason(s) for the termination or suspension. Study participants will be contacted, as applicable, and be informed of changes to study visit schedule.

Circumstances that may warrant termination or suspension include, but are not limited to:

- Determination of unexpected, significant, or unacceptable risk to participants
- Demonstration of efficacy that would warrant stopping
- Insufficient compliance to protocol requirements
- Data that are not sufficiently complete and/or evaluable
- Determination that the primary endpoint has been met
- Determination of futility

Study may resume once concerns about safety, protocol compliance, and data quality are addressed, and satisfy the sponsor, IRB and/or Food and Drug Administration (FDA).

10.1.3 Confidentiality and Privacy

Participant confidentiality and privacy is strictly held in trust by the participating investigators, their staff, and the sponsor(s) and their interventions. This confidentiality is extended to cover testing of biological samples and genetic tests in addition to the clinical information relating to participants. Therefore, the study protocol, documentation, data, and all other information generated will be held in strict confidence. No information concerning the study or the data will be released to any unauthorized third party without prior written approval of the sponsor.

All research activities will be conducted in as private a setting as possible.

The study monitor, other authorized representatives of the sponsor, representatives of the Institutional Review Board (IRB), regulatory agencies or pharmaceutical company supplying study product may inspect all documents and records required to be maintained by the investigator, including but not limited to, medical records (office, clinic, or hospital) and pharmacy records for the participants in this study. The clinical study site will permit access to such records.

The study participant's contact information will be securely stored at each clinical site for internal use during the study. At the end of the study, all records will continue to be kept in a secure location for as long a period as dictated by the reviewing IRB, Institutional policies, or sponsor requirements.

Study participant research data, which is for purposes of statistical analysis and scientific reporting, will be transmitted to and stored at within RedCap Cloud. This will not include the participant's contact or identifying information. Rather, individual participants and their research data will be identified by a unique study identification number. The study data entry and study management systems used by clinical sites and by CRU research staff will be secured and password protected. At the end of the study, all study databases will be de-identified and archived within RedCap Cloud.

10.1.4 Future Use of Stored Specimens and Data

Data will be maintained on RedCap Cloud per institute policy. Stored specimens will be discarded after analysis per Cleveland Clinic Laboratory policy.

12.1 Food Allergy Quality of Life Questionnaire for Parents (1-12 years old)

Supplement 1 A

Food Allergy Quality of Life Questionnaire for Parents (children 1-12 years old)

Instructions: The questions below are about the influence of food allergy on your child's quality of life. It is important that all questions be completed. Answer every question by putting an 'x' in the proper box. You may choose from the following answers:

	1 Not	2 Barely	3 A little	4 Fairly	5 Quite	6 Very	7 Extremely
Because of food allergy, my child feels...							
1. Different from other children							
Because of food allergy, my child has been negatively affected by...							
2. Receiving more attention than other children of his/her age							
3. Having to grow up more quickly than other children of his/her age							
4. His/her environment being more restricted than other children of his/her age							
Because of food allergy, my child...							
5. Experiences physical distress							
6. Experiences emotional distress							
7. Is more anxious in general than other children of his/her age							
8. Is more cautious in general than other children of his/her age							
9. Is not as confident as other children of his/her age in social situations							
10. Wishes his/her food allergy would go away							
11. Has a lack of variety in his/her diet							
Because of food allergy, my child feels...							
13. Anxious about food							
13. Afraid to try unfamiliar foods							
14. Concerned that I am worried that he/she will have a reaction to food							
15. Frustrated by dietary restrictions							
16. Left out of activities involving food							
Because of food allergy, my child's ability to take part has been limited...							
17. By anxiety when going to new places							
18. By concern that he/she must always be cautious about food							
19. By anxiety when eating with unfamiliar adults/children							
20. In social activities in other people's houses (sleepovers, parties, playtime)							
21. In preschool/school events involving food (class parties/treats/lunchtime)							
22. Being upset that family social outings have been limited by food allergy							
23. By frustration from social restrictions							
24. Restaurants we can safely go to as a family							
25. Holiday destinations we can safely go to as a family							
How troublesome did you find side effects of oral immunotherapy (OIT)?							

12.2 Food Allergy Quality of Life Questionnaire for Parents (13-16 years old)

Supplement 1B

Food Allergy Quality of Life Questionnaire for Adolescents (13-16 years old)

Instructions: The questions below are about the influence of food allergy on your quality of life. It is important that all questions be completed. Answer every question by putting an 'x' in the proper box. You may choose from the following answers:

	1 Not	2 Barely	3 A little	4 Fairly	5 Quite	6 Very	7 Extremely
How troublesome do you find it, because of your food allergy, that you...							
1. Must always be alert as to what you are eating?							
2. Are able to eat fewer products							
3. Are limited by the products you can buy							
4. Must read labels							
5. Are less easily able to spontaneously accept an invitation to stay for a meal?							
6. Are less able to taste or try various products when eating out?							
7. Must check yourself whether you can eat something when eating out?							
8. Hesitate eating a product when you have doubts about it?							
9. Must refuse treats at school or work?							
10. That you have to explain to people around you that you have a food allergy?							
11. Have the feeling that you have less control of what you eat when eating out?							
12. Must carry an epinephrine auto injector?							
13. Must be careful about touching certain foods							
14. That the ingredients of a product change?							
15. That the label states, "may contain traces of peanut?"							
16. That the labeling of the bulk packaging (for example box or bag) is different than the individual packages?							
17. That during social activities others can eat the food to which you are allergic?							
18. That during social activities your food allergy is not taken into account enough?							
How frightened are you, because of your food allergy...							
19. Of an allergic reaction?							
20. Of unintentionally eating the wrong food?							
21. To eat something you have never before?							
Please answer the following questions:							
22. How discouraged do you feel during an allergic reaction?							
After completion of study only:							
23. How troublesome did you find side effects of oral immunotherapy (OIT)?							

12.3 Dosing/Adverse Events Recording Sheet

Supplement 2

Dosing/Adverse Events Recording Sheet

Patient Name:

Number:

Date _____	Dose _____	Time of Dose _____			
Any Reaction?  Yes  No					
If yes...					
Symptoms of Reaction? (check all that apply)	 Rash/hives	 Lip/Mouth Itching	 Nausea/Upset Stomach	 Vomiting	 Cough/ Wheeze  Other: Please comment
Treatment Required?	 No	 Yes	If yes, what?	 Antihistamines	 Albuterol  Epinephrine
How soon after dose did symptoms begin?	 Within 5-10 minutes	 10-60 minutes	 60-120 minutes	 >120 minutes	
Location of rash, if present (check all that apply)	 Face	 Neck/Chest	 Arms and/or legs	 Stomach and/or back	
How long were symptoms present before treatment was given?	 <10 minutes	 10-30 minutes	 30-60 minutes	 > 60 minutes	
How many doses of treatment were given?	 1	 2	 3 or more		
How long did symptoms last?	 <10 minutes	 10-60 minutes	 60-120 minutes	 >120 minutes	
Any other comments?					

SUMMARY OF CHANGES

Please provide a list of changes from the previous approved version of the protocol starting at IRB approval. This table will remain blank until initial IRB approval. The list shall be a brief overview. When appropriate, a brief justification for the change should be included. This is a running list for the life of the study.

Protocol Date	Section	Change
04.02.2019	Footer and PSP	Changed Version number and version date to 4.0 and 4-2-19 respectively
	6. Study Intervention	All references to "UH Lerner Tower Kitchen" were replaced with "UH Dahms Clinical Research Unit"
	6. Study Intervention	The ongoing post study OIT maintenance period was changed to being optional for study participants and is not paid for by the study.
	8.2 Study Assessments and Procedures	At Visit 1, the physician and participant will review and update the patient's Food Allergy & Anaphylaxis Emergency Care Plan. Conmed review also added before each dose escalation
	PSP and section 8.3.9	Changed PIRC (Pediatric Institute Review Committee) to PRRC (Pediatric Research Review Committee)
	Inclusion criteria	Added the additional language "within a 12 month period of study enrollment" in the inclusion criteria requiring Evidence of IgE mediated peanut hypersensitivity
	1.3 Schedule of activities and section 6.1	Added Urine Pregnancy
	6.2 IP dispensing	Remove randomize to treat and place a blinded label on jar from.
	Section 7.2	Added additional reasons for discontinuation
	1.3 Schedule of activities	Changed Adverse event review to AE review, added Study drug compliance and conmed assessment lines

Protocol Date	Section	Change
	8.3.1	The CoFAR and CTCAE are mentioned as the scales that will be used to assess SAEs/AEs
	8.4.2 and 8.4.3	Rewording of reporting requirements and timelines
05.28.2019	PSP and footer	Updated amendment # and version date
	Schedule of events, table #4 and table #5	Added spirometry and peak flow measure to study visits
	9.1 Statistical Hypothesis	Added language in regards to safety hypothesis
10.01.2019	PSP and footer	Updated amendment # and version date
	Schedule of Events section 1.3 and section 6.1	Added additional urine pregnancy at visit 10
	Schedule of Events section 1.3	Added language on spirometry being done at investigators discretion at enrollment as well visit 10
	Section 6.1	Clarified that the location of the skin prick test must be the same throughout the study
	Section 6.1 and table 7	Added a 25 mg dose in DBOFC as well as clarification that additional smaller doses may be necessary on a patient by patient basis depending on the results of the initial OFC
	Section 6.1	In build-up phase a dose double the size of the highest tolerated dose in the initial escalation may be used before the patient can be entered into the build-up phase schedule
02.12.2020	Footer	Updated protocol version date and amendment number
	PSP	Added signature line for sponsor
	Inclusion criteria	Added verbiage to inclusion criteria #2 "or a high level of suspicion based on testing at the discretion of the investigator."

Protocol Date	Section	Change
	Initial dose escalation (Table 5)	Removed the first 2 doses in the initial dose escalation (0.1 and 0.2 milligrams of peanut protein). Added a 4mg dose to be given at +90 minutes. Adjusted time for 6mg dose to +120 minutes

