Compare the rate of adverse effects of boiled peanut oral immunotherapy to published data on roasted peanut oral immunotherapy.	
The rate of adverse events in the subjects receiving boiled peanut oral immunotherapy. Possible adverse events include: side effects of treatment defined as oral itching, rhinorrhea, conjunctivitis, urticaria, angioedema, abdominal upset, vomiting, diarrhea, cough, wheeze, or anaphylaxis
 
 • Adverse events will be recorded in terms of the percentage of subjects with adverse events on initial escalation day and at dose escalation visits by CRU staff. • Adverse events will also be recorded in terms of overall percentage of home doses that result in adverse reaction, with data compiled from home logs (Supplement 2). 
The adverse reactions will be graded in severity and the treatment required will be recorded.
 
Validated, age-specific, food-related quality-of-life surveys before and after peanut oral immunotherapy will be completed
	As described above, the rate of adverse events with roasted peanut oral immunotherapy is high. Thus treatment options with less adverse effects are highly desirable. In vitro data has demonstrated that boiled peanut has reduced allergenicity compared to roasted peanut and similar immunogenicity. As such, we anticipate a lower rate of adverse reactions in our subjects compared to published data on roasted peanut OIT.

	by all patients/families ²⁷ (Supplement 1).	
--	--	--

4. Study Design

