7.1 Discontinuation of Study Intervention

Criteria for discontinuing oral immunotherapy in a subject will include:

- Subject nonadherence to OIT, specifically defined by 12 (approximately 10%) nonconsecutive missed doses.
- A life-threatening adverse reaction to OIT, specifically a grade 4 reaction as defined by the Consortium of Food Allergy Research (CoFAR) criteria. See table in Section 8.3.3.1.
- Symptoms suggestive of Eosinophilic Esophagitis (EoE) – i.e. difficulty swallowing, chest pain, persistent heart burn, upper abdominal pain, and/or no response to gastroesophageal reflux disease (GERD) medication

Symptoms suggestive of Eosinophilic Esophagitis (EoE) will prompt discontinuation of oral immunotherapy and begin once weekly symptom monitoring phone calls with study staff. If symptoms fail to resolve after 1 month off therapy, consultation with Gastroenterology will be considered for further evaluation and management.

Discontinuation from oral immunotherapy does not mean discontinuation from the study, and remaining study procedures should be completed as indicated by the study protocol. If a clinically significant finding is identified (including, but not limited to changes from baseline) after enrollment, the investigator or qualified designee will determine if any change in participant management is needed. Any new clinically relevant finding will be reported as an adverse event (AE).

The data to be collected at the time of study intervention discontinuation will include the following:

- Skin prick test to peanut
- Peanut sIgE, peanut component panel, and peanut IgG4

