8.3.3 Classification of an Adverse Event

8.3.3.1 Severity of an Event

All adverse events will be graded in severity utilizing criteria specifically developed by the Consortium of Food Allergy Research.²⁷ These criteria are widely accepted and applied to OIT clinical trials.

Grade 1 Mild	Grade 2 Moderate	Grade 3 Severe	Grade 4 Life threatening	Grade 5 Death
Transient or mild discomforts (< 48 hours), no or minimal medical intervention/therapy required. These symptoms may include pruritus, swelling or rash, abdominal discomfort or other transient symptoms.	Symptoms that produce mild-to-moderate limitation in activity, some assistance may be needed; no or minimal intervention/therapy is required. Hospitalization is possible. These symptoms may include persistent hives, wheezing without dyspnea, abdominal discomfort/increased vomiting or other symptoms.	Marked limitation in activity, some assistance usually required; medical intervention/therapy required, hospitalization is possible. Symptoms may include bronchospasm with dyspnea, severe abdominal pain, throat tightness with hoarseness, and transient hypotension among others. Parenteral medication(s) are usually indicated.	Extreme limitation in activity, significant assistance required; significant medical/therapy. Intervention is required; hospitalization is probable. Symptoms may include persistent hypotension and/or hypoxia with resultant decreased level of consciousness associated with collapse and/or incontinence or other life-threatening symptoms	Death

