9.2.3 Derivation of Safety Variables

Adverse events (AEs) will be categorized by preferred term using the CTCAE Version 5.0, and by the specific AEs of interest listed in section 5.2. The *specific AEs of interest* with possible alternative preferred terms, which will be grouped together, are: oral itching (oral pruritus), rhinorrhea (allergic rhinitis or rhinorrhea), conjunctivitis (eye itching), urticaria (hives), angioedema, abdominal upset (dyspepsia or nausea), vomiting, diarrhea, cough, wheeze (wheezing), and anaphylaxis.

Mortality. Mortality will be identified by an AE of CoFAR severity grade 5, and/or 'Death' indicated as a SAE criteria on the CRF for AEs.

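### The home dosing log has no tick-box for rhinorrhea, conjunctivitis, angioedema or diarrhea and combines cough with wheeze, so symptom-specific home-dose rates may be under-ascertained

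*Protocol*

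**What the plan says.** The secondary safety endpoint in Protocol section 3 lists eleven side effects: "oral itching, rhinorrhea, conjunctivitis, urticaria, angioedema, abdominal upset, vomiting, diarrhea, cough, wheeze, or anaphylaxis". SAP section 5.2 repeats the list. For treatment at home, section 3 asks for the "overall percentage of home doses that result in adverse reaction, with data compiled from home logs".

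SAP 9.2.3 groups AEs under the same eleven terms and keeps the respiratory ones apart: "vomiting, diarrhea, cough, wheeze (wheezing), and anaphylaxis". SAP 11.1 and 11.1.1 tabulate them by patient and by dose, with home doses as a reporting phase of their own. Each of the eleven terms is printed even if nobody had the event. SAP 11.1.2 restricts the preferred terms in the comparison with published trials to these eleven.

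The log is in Protocol 12.3. For each dose it first asks, yes or no, whether there was any reaction. The symptom item that follows, "Symptoms of Reaction? (check all that apply"), offers rash or hives, lip or mouth itching, nausea or upset stomach, vomiting, one box for cough and wheeze together, and "Other: Please comment". A general comments field closes the form.

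**The concern.** The form that feeds the home-dose tables does not match the terms those tables report. Families are prompted for some endpoint symptoms and must volunteer others. Because SAP 11.1.1 prints a row for every term regardless, a zero for diarrhea or angioedema under home doses could mean that it did not happen or that nobody wrote it down. The table would not show which.

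Cough and wheeze raise a different problem: they are recorded but not distinguished. The severity table in Protocol 8.3.3.1 names "wheezing without dyspnea" at grade 2 and does not name cough, so the shared tick does not support grading either. Neither document says how such a tick is coded.

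These rows describe what kind of reactions boiled peanut causes at home, where most doses are taken, and they enter the descriptive comparison with roasted-peanut trials.

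**Working it through.** **Step 1. Match the endpoint terms to the boxes.** Terms are from Protocol section 3 and SAP 9.2.3; boxes are from Protocol 12.3.

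| Endpoint term | Named box on the home log |
|---|---|
| Oral itching | Lip or mouth itching |
| Urticaria | Rash or hives (wider than urticaria) |
| Abdominal upset | Nausea or upset stomach |
| Vomiting | Vomiting |
| Cough | Shared with wheeze |
| Wheeze | Shared with cough |
| Rhinorrhea | None |
| Conjunctivitis | None |
| Angioedema | None |
| Diarrhea | None |
| Anaphylaxis | None |

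Six of the eleven terms reach a named box, two of them through the same box, and five do not. Anaphylaxis is a clinical diagnosis that a parent's tick would not settle, so four missing boxes matter.

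**Step 2. Which rates depend on the boxes?** The protocol's home-dose measure is an overall percentage of doses with a reaction. The yes/no item answers that before any symptom box is reached. The boxes bear on the symptom-specific home rows in SAP Tables 3.1 and 3.2, and on the symptom rows of Table 3.3, which pools home doses with the later escalation visits.

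**Step 3. How many doses does the log cover?** The documents state no figure, so this is built from the schedule in SAP 6.3, Protocol Tables 5 and 7, and the planned 10 children.

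- The initial escalation (SV2) is 1-4 weeks after SV1, and the exit challenge (SV10) is 18 weeks after SV1. Dosing therefore lasts 18 - 4 = 14 to 18 - 1 = 17 weeks, or 98 to 119 days.
- SV2 to SV9 take up 8 clinic dosing days. Home doses per child: 98 - 8 = 90 to 119 - 8 = 111. For 10 children: 900 to 1,110.
- Clinic doses before exit: 5 on the initial day + 7 at escalation visits = 12 per child, 120 in total.
- Exit challenge: up to 6 doses x 2 arms = 12 per child, 120 in total.

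Home share of doses:

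- Comparative table (SAP 11.1.2, exit challenge excluded): 900 / 1,020 = 88% to 1,110 / 1,230 = 90%.
- Dose-level summary (SAP 11.1.1, both exit arms counted): 900 / 1,140 = 79% to 1,110 / 1,350 = 82%.

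**Step 4. What would one missed entry do?** At dose level, one unrecorded episode moves a home rate by 1/1,110 = 0.09 to 1/900 = 0.11 percentage points. At patient level, if it was that child's only episode, the figure moves by 1/10 = 10 percentage points. These show sensitivity only. Nothing in the documents says how many entries would be missed.

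**The case against.** The log is not the only route by which a home reaction reaches the data. Besides the free-text option and the comments field, Protocol 8.3.4 has the investigator ask about AEs at every visit and enter all of them on a case report form with an event description. Protocol 8.3.7 has a physician investigator discuss the nature and severity of home AEs by phone. Protocol 5.3 tells families to contact the investigators about illness or significant rhinitis symptoms. A clinician's description can supply a term that has no box and can separate cough from wheeze. All of this stands, and it limits the point to a risk in the symptom-specific rows. What remains is that these routes are unstructured, and neither document says how log entries, free text and the AE form are reconciled when doses are counted.

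Three stronger readings are tempting, and the documents do not support them.

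- A reader might infer that the overall home-dose reaction rate is compromised. The yes/no item captures it without reference to the boxes. A family might still overlook a mild unprompted symptom, hence largely rather than wholly unaffected.
- A reader might infer that unlisted symptoms are certain to be under-counted and that this tilts the comparison with roasted peanut towards the study hypothesis. Under-counting is plausible but not shown. Its effect on the comparison depends on how the published trials prompted families, which the documents do not describe. That comparison is also descriptive, without testing.
- A reader might infer that the log should also prompt for the eosinophilic esophagitis symptoms in Protocol 7.1 ("difficulty swallowing, chest pain, persistent heart burn, upper abdominal pain"). These are discontinuation criteria and not among the eleven endpoint terms, and the log records reactions to single doses.

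**Conclusion.** The mismatch between form and tables is certain. Four endpoint symptoms that a family could report have no box, two share one, and the SAP reports all six separately for home doses. The consequence is a possibility: symptom-specific home rates may be under-ascertained for rhinorrhea, conjunctivitis, angioedema and diarrhea. For cough and wheeze, separate home rates cannot be obtained from the tick alone.

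The home shares in the working assume the protocol schedule, 10 children, no dropout, no missed doses, one dose per escalation visit and, for the lower range, all six exit doses in both arms. Real timing may differ, since SAP 6.3 places no limits on visit timing in the primary analysis. The shares measure how much of the dosing depends on the log and do not estimate bias. The primary efficacy endpoint is untouched. This is a worthwhile, cheap improvement to the secondary safety endpoint.

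**What to change.** Revise Supplement 2: add boxes for runny nose, itchy or red eyes, swelling of lips or face, and diarrhea, and split cough from wheeze. Derive anaphylaxis from clinician review and say so in SAP 9.2.3.

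SAP 11.4 describes spirometry and peak flow in the past tense, so some logs may already be complete. For those, add a short rule to the SAP:

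- Assign a combined cough/wheeze tick to cough or wheeze from the AE case report form description where there is one. Otherwise report a combined cough-or-wheeze row for home doses.
- Footnote the terms without a box as spontaneously reported in Tables 3.1 to 3.3, so that a zero is not read as a prompted negative.

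The cost is a one-page form revision with IRB notification and matching case report form fields, plus a few lines in the SAP. The downside is a slightly longer daily log and possibly a higher recorded AE rate.
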